## 2. INTRODUCTION

### 2.1 Background Information

There is strong evidence that the first few years of life build the foundations for future health and wellbeing and that taking a preventative approach together with systems changes in local agencies, can improve the life chances of babies and children. However, these interventions have yet to be tested at scale. The Big Lottery Fund has invested £215M in funding A Better Start (ABS) in order to improve understanding about effective early childhood intervention in five competitively selected areas across England: Bradford, (led by Bradford Trident); Blackpool (led by the National Society for the Prevention of Cruelty to Children - NSPCC); Lambeth (led by National Children's Bureau - NCB); Nottingham (led by Nottingham City Care), and; Southend-On-Sea (led by the Pre-School Learning Alliance). These geographical areas have a high level of need in terms of deprivation, and child health.

Big Lottery Fund aims to use the learning from this investment to promote a shift in public policy, public funding and agency culture away from remedial services to greater investment in prevention in pregnancy and the first few years of life. Each area will deliver science- and evidence-based preventative programmes, policies and services, with a focus on the most disadvantaged families. Investment will take place in antenatal and postnatal support programmes that set out to achieve one or more of the following: (i) improve a child's social and emotional development – preventing harm before it happens (including abuse and neglect, perinatal mental health problems and domestic violence) as well as encouraging parenting practices that promote attachment; (ii) improve their language development by encouraging parents to talk, read and sing to, and particularly to praise – their babies and toddlers, and by ensuring local childcare services emphasise language development; and (iii) improve their nutrition and reduce obesity by encouraging breast-feeding and promoting good nutritional practices. The evidence suggests that these three areas can have a significant impact on long-term life chances and outcomes.

Each area will also address systems change across all children and families' agencies. The systems changes should deliver less bureaucratic, more joined-up services; services that are prevention-focused; that are needs- and demand-led; that work for a whole family; and that get it right for families first time.

Big Lottery Fund has invested in the Warwick Consortium, led by the University of Warwick, to conduct a 10-year study designed to evaluate the impact of ABS across these five selected intervention areas, compared with matched comparison sites.

In addition to the impact evaluation, Warwick Consortium are also undertaking an implementation evaluation involving the collection of process data from the participating sites, and a learning and dissemination work-stream to ensure that the lessons in terms of what works, for whom, and why, are identified and widely disseminated.

### 2.2 Warwick Consortium: The Team

Warwick Consortium is led by [name], and comprises a team that includes both substantive and methodological expertise, and that will enable it to successfully evaluate and disseminate the learning from ABS. Jointly, it has a strong track record in conducting multi-strand evaluations of complex programmes, and in combining the methodologies required for this including: longitudinal surveys, impact analysis using survey and administrative data, randomised controlled trials (RCTs), cost-effectiveness measurement, qualitative interviews, and analysis. The team includes field leaders in terms of socio-emotional development ([name]), nutrition ([name]) and early years education ([name]). There is also academic expertise in biometric measurement ([name]), childbirth and the perinatal period ([name]), implementation research ([name]) economic evaluation ([name]), and longitudinal evaluation and analysis ([name]).

The core team (responsible to the day-to-day running of the evaluation) includes the Universities of Warwick and Oxford, along with Ipsos MORI (evaluation fieldwork), Bryson Purdon Social Research (BPSR) (analysis) and ECORYS UK (learning and dissemination).

The evaluation is project-managed by [name], based at the University of Oxford.

### **3. RATIONALE FOR A BETTER START**

Big Lottery Fund's decision to invest in preventative early intervention is both important and timely. There is a strong growing body of evidence supporting the need for preventative early intervention, particularly during pregnancy and the first three years of life. Below is a summary of the evidence regarding the factors that are associated with good or compromised outcomes in terms of nutrition, socio-emotional development and educational achievement (including language and speech) during the first three years of life. This research has informed the design of the evaluation, including the proposed choice of outcomes to be measured, and the time points at which these are assessed.

Briefly stated (providing selected references only):

#### **3.1 Poverty**

Despite improvements in absolute levels of poverty and universal access to education and healthcare, poverty continues to be a significant predictor of compromised functioning in terms of nutritional and psychological wellbeing and educational outcomes (Marmot 2008). However, the research shows that the effects of poverty on these outcomes are almost entirely mediated by parental care, which provides considerable opportunity for remediation and interventions.

#### **3.2 Early Years Developmental and Biological Factors**

Research increasingly supports the view that the origins of much adult disease lie in the 'developmental and biological disruptions occurring during the early years of life' (Shonkoff, Boyce, McEwen, 2009), and more specifically as a result of the 'biological embedding of adversities during sensitive developmental periods' (p.2009). This research suggests that the brain plays a central role in this process because it 'interprets and regulates behavioural, neuroendocrine, autonomic and immunological responses to adverse events, serves as a target of acute and chronic psychosocial and physical stress, and changes both structurally and functionally as a result of significant adversity'. For example, children's exposure to the type of 'toxic stress' (i.e. recurrent physical and/or emotional abuse, chronic neglect, parental substance misuse and domestic violence, severe mental health problems) that is more common in families living in poverty, also leads to changed brain architecture and reduced thresholds for stress, that continue throughout the life course, increasing the risk of stress-related disease and cognitive impairment.

The two key sensitive periods are pregnancy and the first three years of life because pre- and post-natal stress cause alterations in the function of the hypothalamic-pituitary-adrenal axis, which makes the hormone cortisol, leading to increased production (Glover, O'Connor & O'Donnell, 2010). This underlies some of the alterations in foetal and child brain neurodevelopment following early exposure to stress, and may also be one of the mediators of an altered epigenetic profile (see below).

#### **3.3 Genotypes**

Recent research on differential susceptibility has found that children's genotypes interact with their caregiving environment to influence the impact of early caregiving. For example, gene x environment studies show that children with a short 5-HTTLPR allele have very unfavourable outcomes when parenting is compromised, but that these children also have significantly better outcomes than usual when parenting is better than average (Kochanska et al., 2011).

### 3.5 Attachment

Attachment appears to be one of the key mechanisms by which children regulate their emotional states, particularly when they are stressed (e.g. Sroufe, 2005). There is now incontrovertible evidence showing that securely attached children experience a range of improved outcomes, and that insecure and particularly disorganised attachment, are both associated with less optimal functioning. Disadvantaged children have considerably higher rates of both insecure and disorganised attachment.

## 4. OBJECTIVES

### 4.1 Evaluation Objectives

The overall aim of this research evaluation is to provide robust evidence about the impact and cost-effectiveness of the Big Lottery Fund ABS Programme, focusing predominantly on pregnancy and the first three years of life, identifying what interventions work, for whom, and under what circumstances.

The survey tools have been designed using a range of validated and standardised measures across three domains: socio-emotional health; nutrition; speech, language and learning.

The impact and economic evaluation will assess short- (birth – 3 years), and medium- (4-5 years) outcomes in each of the three key outcome domains. It will also measure parental outcomes that are strong predictors of infant/child functioning.

The impact and economic evaluation of ABS will address the following research questions:

- I. How effective is ABS in improving children's socio-emotional functioning; nutrition; and language?
- II. How cost-effective is ABS?

The evaluation of the ABS programme will also provide answers to the following questions:

- III. How quickly do we find improvements in outcomes, and how sustainable are these over time?
- IV. How does this compare with families in other areas not supported by Big Lottery Fund's investment?
- V. Is the programme investment worthwhile?
- VI. How much does it cost to run the programme, including the initial set-up, and over time?
- VII. How cost-effective are different approaches in terms of the outcomes achieved?

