## 5. DESIGN AND METHODOLOGY

### 5.1 Study Design and Timescale

Central to the Impact evaluation is a longitudinal study based on a series of surveys of parents and children in both intervention and matched comparison areas. It will begin in 2015, firstly with the piloting of questionnaires over a 3-month period across two of the intervention areas (Lambeth and Southend), prior to the collection of baseline data from families of 1, 2 and 3-year-olds across all intervention and comparison sites. This will generate data on all proposed parent and child outcomes (up to when the children are aged 3) prior to the implementation of *A Better Start* in the five sites. Before running the main longitudinal study, the Consortium will run a small pilot in all intervention areas and five comparison areas, to test its recruitment and early data collection methods. This will take place in 2016.

The cohort study will begin in 2019 and end in 2026. All elements of the study will be replicated in matched comparison areas to generate counterfactual estimates. During its life cycle, the study will use a wide-range of data collection methods (listed in Table 1) to track families from mid-pregnancy until the children are aged 5 years. The primary data collection methods will be face-to-face interviews undertaken by trained and experienced Ipsos MORI field researchers, either in families' homes or other place of their choice - e.g. Children's Centres – (up to age 3), followed by parental online and/or postal surveys, and in-school teacher assessments when children are 5-years of age.

The study has been designed to generate a significant amount of evidence, key elements of which are:

- Data from within programme areas will be used to measure and quantify short-, medium- and longer-term outcomes for the families who are being targeted by the interventions, and to establish how these evolve over time, from pre-programme to late programme;
- Data from within comparison areas will generate estimates of the counterfactual outcomes for matched parents and children who are not receiving the interventions, but are receiving standard services;
- For both intervention and comparison areas, the implementation data about how parents use and experience services, will generate an understanding about how any intervention impacts have been achieved;

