- For both intervention areas and selected comparison areas (e.g. the closest matched comparison area per intervention area), early years services data will generate an understanding about systems change within early years provision and help us determine whether any changes detected over time are due to ABS or occur for another reason;
- Administrative data on child and family outcomes in the five ABS areas against those in other similar matched areas, will provide estimates of the impact of the programmes across the whole of the eligible population, to test whether the work of the five areas has area-wide impacts;
- Data on costs and services from the five areas will be combined with our findings on the impact of the programme, which will permit us to measure the cost-effectiveness of the programme, both overall and for each site.

The data collection within intervention and comparison areas comprises two components:

1. Cross-sectional, baseline surveys of parents of 1, 2 and 3 year-olds in the first year of the programme (2016/17), which will provide baseline data on outcomes for current parents and children in all our areas prior to the implementation of A Better Start. Baseline surveys will be conducted in both intervention and matched comparison areas, allowing us to (a) check that the intervention and comparison areas are the same prior to the start of the programme; and (b) to allow us to measure changes in outcomes over time in both the intervention and comparison areas.
2. A large cohort study, starting recruitment in 2019, which will generate data on impact. Families will be tracked until the children are 5-years of age. In addition to parent and teacher-report data, we will collect additional data for a sub-sample of families, using measures that will provide valuable information, but which are too costly to collect and/or process across the entire sample.

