**Table 1. Summary of main evaluation timeline, data collection methods and time-points**

Year	Stage involved	Mother / main carer	(Brief resident) Partner Q'aire	Additional assessments
BASELINE DATA COLLECTION				
2016/17	Baseline	Face-to-face interview of families with children of ages 1,2 & 3	x	x
2016/17 PILOT PARTICIPANT IDENTIFICATION & RECRUITMENT METHODOLOGY				
	26-36 weeks' pregnant	Face-to-face interview	✓	x

	Baby aged 2-months	Short online or postal survey	x	x
	Baby aged 4-months 	Short telephone interview or online survey	x	x
COHORT STUDY				
2019/20	26-36 weeks' pregnant	Face-to-face interview	✓	x
2019/20	At birth		x	Hair Sample from mother (to measure cortisol)
2019/20	Baby in first week of life		x	Cheek (Buccal) Swab (for epigenetic purposes)
2019/20	Baby aged 4-months	Short telephone interview or online survey	x	x
2020/21	Child aged 1	Face-to-face interview at home	✓	CARE Index (video clip of child playing to assess parent-child interaction)
2021/22	Child aged 2	Face-to-face interview at home	✓	From the child: both hair sample (cortisol) and a cheek swab (to measure epigenetic changes)
2022/23	Child aged 3	Face-to-face interview at home	✓	
2024/25	Child aged 5	Postal or online survey Schools Data	x	video-recorded MCAST measure of child attachment – carried out in school by trained researcher

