As data build up from the longitudinal study we will start to create multiple datasets that can then be analysed in multiple ways. Much of the analysis will be child-age-specific and will use the data cross-sectionally. For instance, when looking at the impact of the programme by age 3, comparisons will be made across six independent samples: baseline, cohort 1, and cohort 2, in both programme and comparison areas. The sorts of questions this will answer will be whether change since baseline in age 3 outcomes has been greater in programme areas than in comparison areas. Other analyses will make more direct use of the longitudinal nature of the two cohorts: such as 'have children in programme areas followed different trajectories over their early years than children in comparison areas'. Or, 'to what degree can outcomes at age 3 be explained by earlier experiences of the parent and child'.

We envisage that most of our analysis of impact will be based on comparisons between programme and comparison area groups that have been balanced on confounding variables using propensity score matching. That is, each time the comparison area data is used to generate an estimate of the counterfactual, differences between the background characteristics of the two groups (programme and comparison) will be established using regression modelling (either probit or logistic regression)

and a 'propensity' to be in the programme group estimated. The two groups will then be matched on this propensity score. This will ensure a reasonably close match in the two groups on the full range of background characteristics. If there is evidence of biasing non-response effects in the cohorts over time then weighting of the data to try and remove any such bias will be considered. All statistical tests and standard errors will be calculated taking into account the matching, non-response weights, and between-comparison-area effects.

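### Question III can be answered by child age for one birth cohort but, from the surveys, not by time since programme start, and the analysis section assumes a second cohort that the design lacks

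*Protocol*

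**What the plan says.** Section 4.1 lists as question III "How quickly do we find improvements in outcomes, and how sustainable are these over time". It does not say whether time means the child's age or years since the programme began. Section 5.1 leans towards the second: data from programme areas are meant "to establish how these evolve over time, from pre-programme to late programme".

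The survey design in Section 5.1 has two components:

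- "Cross-sectional, baseline surveys of parents of 1, 2 and 3 year-olds in the first year of the programme (2016/17"), described as preceding implementation;
- "A large cohort study, starting recruitment in 2019, which will generate data on impact".

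Table 1 gives the cohort one calendar period per age: age 1 in 2020/21, age 2 in 2021/22, "2022/23 Child aged 3", and age 5 in 2024/25.

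Section 6.2 describes something different. For impact by age 3, "comparisons will be made across six independent samples: baseline, cohort 1, and cohort 2, in both programme and comparison areas", and it refers to two cohorts again when it turns to longitudinal analyses. It says that "Much of the analysis will be child-age-specific and will use the data cross-sectionally", and that differences in background are modelled and the groups matched on a propensity score "each time the comparison area data is used to generate an estimate of the counterfactual". Non-response weighting will be considered if there is evidence of bias.

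**The concern.** Suppose the impact is larger at age 3 than at age 1. With one birth cohort, the reason could be that the effect grows as children develop, or that services in 2022/23 were better established than in 2020/21. If the result is reported as the answer on speed and sustainability, readers may take it as a statement about how fast the programme came to work. The data do not support that.

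The second problem is composition. If each age is analysed on its own matched sample, and the families available shrink between ages, an apparent fade-out or growth may partly be a change in the families compared.

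The reference to a second cohort makes both worse. It suggests that the analysis was written for a design that could have separated age from programme year, and that the design changed without the analysis text following.

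**Working it through.** **1. The plan's own figures.** Section 5.5.3 gives detectable effects at 80% power. I assume two-sided alpha 0.05 (not stated), SD 1 and no design effect, so the detectable effect is (1.960 + 0.842) × √(Σ 1/n).

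- Age 1, cells 500, 270, 1200, 825: 2.802 × √0.007749 = 0.247 (stated 0.25).
- Age 2, cells 500, 270, 1060, 720: 0.251 (stated just over 0.25).
- Age 3, cells 500, 270, 815, 555: 0.262 (stated 0.26).
- Age 1, cohort only, 1200 and 825: 0.127 (stated 0.13).

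All reproduce. No number in the plan is disputed here.

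**2. Age against programme year.** Count programme year as years since the 2016/17 baseline, using Table 1.

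| Child age | Period | Programme year |
|---|---|---|
| 1 | 2020/21 | 4 |
| 2 | 2021/22 | 5 |
| 3 | 2022/23 | 6 |
| 5 | 2024/25 | 8 |

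Programme year = age + 3 in every row. Write impact as a + b·age + c·year. Substituting gives (a + 3c) + (b + c)·age, so only the sum b + c can be estimated. The matrix with columns 1, age and year has rank 2 of 3, and the correlation of age with year is exactly 1.00. The baseline precedes implementation, so it adds no impact cell and the rank stays at 2. Between 2016/17 and 2020/21 no outcome at ages 1 to 3 is surveyed.

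For illustration only, a second cohort two years earlier (my assumption; the protocol gives no date) would raise the rank to 3 and lower the correlation to 0.83. That is what the two-cohort text in Section 6.2 could deliver and the design in Section 5.1 cannot.

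**3. Who contributes at each age (Table 2).**

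- Age 1: 1200 + 825 = 2,025. Age 2: 1060 + 720 = 1,780. Age 3: 815 + 555 = 1,370.
- Loss from age 1 to age 3: 1 − 1370/2025 = 32.3%.
- Retention from recruitment to age 3: 815/1715 = 47.5% (programme) and 555/1170 = 47.4% (comparison).

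Section 5.4.3 also excludes families who move out of the areas, so composition changes by rule as well as by non-response.

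**4. Precision for a change in impact from age 1 to age 3.** Assume the same SD-scaled outcome at both ages, every age-3 family also seen at age 1, and within-child correlation ρ. The variance is the sum over the two groups of 1/n₁ + 1/n₃ − 2ρ/n₁.

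- Cohort only: 0.20, 0.17, 0.15 and 0.13 SD at ρ = 0, 0.3, 0.5 and 0.7.
- Difference-in-differences, adding the Section 5.5.1 baselines at age 1 (378 and 225) and age 3 (208 and 216): 0.41 SD at ρ = 0, falling to 0.38 SD at ρ = 0.7.

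These ignore clustering by area and are lower bounds. The Section 5.5.1 baselines are not the 500 and 270 used in Section 5.5.3.

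**The case against.** A reader might infer that question III cannot be answered at all. The documents do not support that. Section 4.1 itself defines short and medium term by the child's age. The cohort is followed at 4 months and at 1, 2, 3 and 5 years alongside comparison areas, and Section 6.2 plans to compare trajectories between the two. Read by child age, the question is answerable for this birth cohort. For children exposed from pregnancy, age and length of exposure coincide in any birth cohort, so that is no fault of this plan. Concurrent comparison areas also absorb general calendar change. What remains inseparable is age from programme maturity.

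Nor is programme time left without a source: Section 5.1 plans area-wide administrative comparisons. Early-programme births are not wholly unsurveyed either, since the recruitment pilot follows babies to 4 months, though without outcomes at ages 1 to 3 and without a formal comparison.

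A reader might also infer that the groups will be re-matched at every wave on whoever is left, and that this biases the results. The protocol does not say so in those words. Re-matching is the natural reading of the Section 6.2 text, but that section leaves when and how to match to a plan written before each analysis phase and allows for non-response weighting. Planned retention from age 1 to age 3 is nearly equal in the two groups (815/1200 = 67.9%; 555/825 = 67.3%). Equal rates do not show that the same kinds of family remain, but the figures do not show bias.

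These objections narrow the point. They do not remove the collinearity or the contradiction over the number of cohorts.

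**Conclusion.** The concern holds in a limited form. The surveys can describe how impact varies with child age in one birth cohort. They cannot say how quickly effects appeared after the programme began, or separate child age from programme maturity. This follows from the Table 1 calendar and needs no statistical assumption. Section 6.2 contradicts Section 5.1 and Table 1 on the number of cohorts, and the missing cohort is the feature that would have helped.

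The composition point is a risk, not a demonstrated bias: up to 32% of those in the age-1 contrast are absent at age 3, and nothing in the protocol ties the age-specific effects to a common population. The baseline covers ages 1 to 3 only, so a claim of sustained effect at age 5 has no difference-in-differences behind it. On the headline estimator, a change in impact between ages 1 and 3 would need to be about 0.4 SD to be detected reliably, under the assumptions above, against 0.25 SD planned for the impact itself. The text should be corrected before the analysis plan for the first cohort wave. It does not undermine the age-specific impact estimates.

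**What to change.** (a) Reconcile Section 6.2 with Section 5.1 and Table 1 on the number of cohorts.

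(b) Restate question III as the age profile of impact in the single birth cohort, and say that age and programme maturity cannot be separated. Answer speed since programme start only from the administrative comparison already planned in Section 5.1, where yearly series exist. The protocol does not show that they do for the study wards, and Section 5.2.6 expects the age-5 school profile to be withdrawn.

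(c) For any comparison of cohort effects across ages, define one target population, the recruited programme-area cohort. Combine balancing weights with wave-specific attrition weights to that target. Weights fixed at recruitment alone would not be enough, because they ignore drop-out. Limit cross-age comparison to outcomes measured with the same instrument (for example ASBI at 2, 3 and 5 years), or label the results clearly as standardised effects: Section 5.7.2 changes the language measure at each of ages 1, 2 and 3. Add a sensitivity analysis in families seen at every wave.

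Keep the difference-in-differences as the age-specific headline. Its baseline families are separate from the cohort, so cohort weights cannot be carried over to them.

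The cost is text changes, modest extra modelling, some precision lost to weighting, and giving up the survey-based claim about speed since programme start. No new fieldwork is needed.
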